Vital signs, pulse oximetry	X		X ^d	X ^o		X ^{d,o}	X		X ^d	X ^o		X ^{d,o}	X		X ^d	X ^o		X ^{d,o}	X	X ^o
12-lead ECG ^e	X																			
Adverse events review																				
Serious adverse events review																				
Prior/concomitant medication																				
LOCAL LABORATORY ASSESSMENTS																				
Pregnancy test ^f	X																			
CBC with differential	X		X	X ^o		X ^o	X		X	X ^o		X ^o	X		X	X ^o		X ^o	X	X ^o
Coagulation	X		X	X ^o		X ^o	X		X	X ^o		X ^o	X		X	X ^o		X ^o	X	X ^o
Chemistry panel	X		X	X ^o		X ^o	X		X	X ^o		X ^o	X		X	X ^o		X ^o	X	X ^o
Urinalysis				X ^o									X							
OTHER ASSESSMENTS/PROCEDURES																				
Gastroscopy ^g													X ^g							
CENTRAL LABORATORY ASSESSMENTS																				
STUDY TREATMENT AND OTHER ASSESSMENTS / PROCEDURES																				
Imaging	See Table 1-3 - imaging assessments																			
AMG 910 short-term IV infusion	X			X ^o		X		X ^o		X		X ^o		X		X ^o		X		X ^o
Observation	Until 4 hours after EOI on day 1		Until 4 hours after EOI on day 3 ^o		Until 4 hours after EOI on day 8		Until 4 hours after EOI on day 10 ^o		Until 4 hours after EOI on day 15		Until 4 hours after EOI on day 17 ^o		Until 4 hours after EOI on day 22		Until 4 hours after EOI on day 24 ^o					

Page 2 of 5

Abbreviations and footnotes defined on last page of table

Table 1-1. Schedule of Activities

Week	Treatment Cycle 3											
	1			2			3			4		
Cycle Day	1		2		8		15		22			
	PRE	0	EOI	4	24	PRE	0	EOI	8	PRE	0	EOI
GENERAL AND SAFETY ASSESSMENTS												
Clinical evaluation ^c	X			X	X	X			X	X		X
Vital signs, pulse oximetry	X			X ^d		X		X ^d	X		X	X
12-lead ECG ^e	X											
Adverse events review												
Serious adverse events review												
Prior/concomitant medication												
LOCAL LABORATORY ASSESSMENTS												
Pregnancy test ^f	X											
CBC with differential	X			X		X			X	X		X
Coagulation	X			X		X			X	X		X
Chemistry panel	X			X		X			X	X		X
Urinalysis	X								X			
CENTRAL LABORATORY ASSESSMENTS												
STUDY TREATMENT AND OTHER ASSESSMENTS / PROCEDURES												
Imaging	See Table 1-3 - imaging assessments											
AMG 910 short-term IV infusion	X					X			X			X
Hospital Stay (Day 1 only)	Until 24 hours after EOI on day 1											
Observation												

Abbreviations and footnotes defined on last page of table

Page 3 of 5

Table 1-1. Schedule of Activities

	Treatment Cycles 4 through 6 ^l												EOT ^j	SFU	LTFU	
	1	2			3			4								

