Week	1	2	3	4	15	22	28									
Cycle Day	1	8			15	22	28									
Hour (relative to EOI ^b)	PRE	0	EOI	4	PRE	0	EOI	4	PRE	0	EOI	4	PRE	0	EOI	
GENERAL AND SAFETY ASSESSMENTS																
Clinical evaluation ^c	X		X	X		X	X		X	X		X	X	X		
Vital signs, pulse oximetry	X		X	X		X	X		X	X		X	X	X		
12-lead ECG ^e	X															
Adverse events review					Continually throughout study											
Serious adverse events review					Continually throughout study											
Prior/concomitant medication					Continually throughout study											
Survival Status and/or subsequent cancer therapy																X
LOCAL LABORATORY ASSESSMENTSⁿ																
Pregnancy test ^f	X															X
CBC with differential	X		X	X		X	X		X	X		X	X	X		
Coagulation	X		X	X		X	X		X	X		X	X	X		
Chemistry panel	X		X	X		X	X		X	X		X	X	X		
Urinalysis	X						X									
CENTRAL LABORATORY ASSESSMENTS																
STUDY TREATMENT AND OTHER ASSESSMENTS / PROCEDURES																
Imaging					See Table 1-3 - imaging assessments											
AMG 910 short-term IV infusion	X			X		X		X		X		X				
Observation		Until 4 hours after EOI on day 1			Until 4 hours after EOI on day 8			Until 4 hours after EOI on day 15			Until 4 hours after EOI on day 22					

Page 4 of 5

Abbreviations and footnotes defined on last page of table

Table 1-1. Schedule of Activities

	Treatment-free Intervals after Cycles 2 and 4 (2 weeks) ^m	
Week	1	2
Day ^k (out of 14-day treatment-free interval)	1	8
GENERAL AND SAFETY ASSESSMENTS		
Clinical evaluation ^c	X	X
Vital signs, pulse oximetry	X	X
Adverse events review	Continually throughout study	
Serious adverse events review	Continually throughout study	
Prior/concomitant medication	Continually throughout study	
LOCAL LABORATORY ASSESSMENTS		
CBC with differential	X	X
Coagulation	X	X
Chemistry panel	X	X
Urinalysis	X	
OTHER ASSESSMENTS / PROCEDURES		
Imaging	See Table 1-3 - imaging assessments	

Page 5 of 5

AE = adverse event; CBC = complete blood count; ECG = electrocardiogram; EOI = end of infusion; EOT = end of treatment; IV = intravenous; LTFU = long-term follow-up; MRI = magnetic resonance imaging; PK = pharmacokinetic; Pre = pre-infusion; SAE = serious adverse event; SCR = screening; SFU = safety follow-up; ctDNA = circulating tumor DNA; PB = peripheral blood

^a All screening procedures should be performed within 21 days prior to cycle 1 day 1 dosing if not stated differently in Section 8.1.1.

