Hospitalization Guidance	
All subjects will be hospitalized for intensive monitoring for the times given below. The subjects may be discharged after these hospitalization periods if there are no grade ≥ 2 adverse events at least possibly related to AMG 910. Minimum hospitalization times for subjects will be as follows:
 
• cycle 1:
– during eIV infusion for a minimum of 4 days– 48 hours after dosing on day 8– 24 hours after dosing on days 15 and 22 with weekly dosing (on days 10, 17, and 24 in cohorts with twice weekly dosing)• cycle 3:
– 24 hours after dosing on day 1• for cycles 1 and 3: study sites must have immediate access to a medical intensive care unit staffed by critical care providers• cycles 2, 3, 4, 5, and 6: subject should be monitored intensely in hospital or outpatient clinic for at least 4 hours after end of each infusion (except cycle 3 after dosing on day 1, see above) and for 8 hours after end of infusion on cycle 3 day 8• cycles 2, 4, 5 and 6: hospitalization not required unless a subject experiences an adverse event requiring hospitalization as described in Table 6-3, or if clinically indicated• re-start of treatment after an interruption due to adverse event: Refer to Table 6-3 
in case of retreatment the same hospitalization guidance applies as for initial treatment at the dose level and schedule to be administered.

Page 2 of 2

DLRT = Dose Level Review Team; eIV = extended intravenous; IV = intravenous; PICC = peripherally inserted central catheter.

^aAMG 910 will be manufactured and packaged by Amgen and distributed using Amgen clinical study drug distribution procedures.

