2	Therapy or infusion interruption indicated but responds promptly to symptomatic treatment (eg, antihistamines, NSAIDs, narcotics, IV fluids); prophylactic medications indicated for ≤ 24 hours	Immediate interruption/delay until event has improved to grade ≤ 1	
Increase monitoring of vital signs as medically indicated until the subject is deemed medically stable
 
Consider slowing infusion rate to deliver the dose over 90 minutes for next dose
 
Monitoring^d following a grade 2 event of IRR:
 
 the subject must be monitored for all subsequent dose administrations for a duration of time that is at least as long as the time it took for the onset of the last IRR plus 4 hours or per the protocol monitoring instructions, whichever is longer. also, considering the 2-week treatment free period after cycles 2 and 4, the subject must be monitored for a duration of time that is at least as long as the time it took for the onset of the last IRR plus 4 hours or per the protocol monitoring instructions, whichever is longer independent of non-occurrence of events in the prior treatment 
This monitoring requirement should be followed until there is no reoccurrence of IRR, at which time monitoring for subsequent doses should follow per protocol post-infusion monitoring.
 
If a subsequent IRR occurs, then the event should be managed and monitored as per protocol, i.e., until it resolves to grade ≤1.
	
 Re-start possible, if successfully managed and improvement to ≤ grade 1 in ≤ 14 days. In case of infusion interruption, continue treatment with next scheduled infusion, do not resume prior infusion or administer delayed infusion. Delay of the next infusion: 
 ≤ 72 hours: follow the SoA for the cycle day on which the infusion was originally planned. The next infusions should then be administered in line with the planned dosing schedule. > 72 hours: Starting with the cycle 1 day 8 infusion and later dosing time points skip the infusion (twice weekly dosing schedule only) and resume SoA for the next scheduled infusion. Hospitalization: at least 48 hours (see also Monitoring^d in the Specific Management section) Dose modification: resume at the same dose Additional measures: additional assessments as indicated in Section 6.2.2.3.4 	If not improved to ≤ grade 1 in ≤ 14 days

Abbreviations and footnotes defined on last page of table

Page 1 of 17

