2	
Symptoms require and respond to moderate intervention
 
 • Oxygen requirement < 40%, OR • Hypotension responsive to fluids or low dose of 1 vasopressor, OR • Grade 2 organ toxicity or grade 3 transaminitis per CTCAE criteria 	
Immediately interrupt/ delay AMG 910 until event improves to CRS grade ≤ 1.
 
elV infusion: Avoid treatment interruption
	
Administer:
 
 • Symptomatic treatment (eg, paracetamol/ acetaminophen for fever) • Supplemental oxygen when oxygen saturation is < 90% on room air • Intravenous fluids or low dose vasopressor for hypotension when systolic blood pressure is < 85 mmHg. Persistent tachycardia (eg, > 120 bpm) may also indicate the need for intervention for hypotension. • If hypoxia or hypotension lasts > 24 hours manage as grade 3 CRS 
Monitor for CRS symptoms including vital signs and pulse oximetry at least Q2 hours for 12 hours and until resolution to CRS grade ≤ 1.
 
Investigators should consider use of tocilizumab^c as an additional therapy in this setting at a dose of 8 mg/kg as a single dose.
 
For subjects with extensive co-morbidities or poor performance status, manage per grade 3 CRS guidance below.
 
Monitoring^d following an event of CRS:
 
 • the subject must be monitored for all subsequent dose administrations for a duration of time that is at least as long as the time it took for the onset of the last CRS plus 4 hours or per the protocol monitoring instructions, whichever is longer. • also, considering the 2-week treatment free period after cycles 2 and 4, the subject must be monitored for dose 1 cycle 3 and dose 1 cycle 5 for a duration of time that is at least as long as the time it took for the onset of the last CRS plus 4 hours or per the protocol monitoring instructions, whichever is longer independent of non-occurrence of events in the prior treatment 
This monitoring requirement should be followed until there is no reoccurrence of CRS, at which time monitoring for subsequent doses should follow per protocol post-infusion monitoring.
 
If a CRS occurs, then the event should be managed and monitored as per protocol, i.e., until it resolves to grade ≤ 1.
	
 • Re-start possible if successfully managed and improved to ≤ grade 1 within 7 days. • Consult with Amgen Medical Monitor first. • In case of infusion interruption, continue treatment with next planned dose, do not resume prior infusion or administer delayed infusion. For elV infusion administration: In case the interruption does not exceed 24 hours, the infusion can be restarted at the same dose without additional measures. If the interruption exceeds 24 hours, the restart of the infusion should be performed under the supervision of the investigator or designee and premedication as described in Section 6.1.4 should be administered if implemented for start of elV infusion. • Delay of next infusion: 
 – ≤ 72 hours: follow the SoA for the cycle day on which the infusion was originally planned. The next infusions should then be administered in line with the planned dosing schedule. – > 72 hours: For the cycle 1 day 8 infusion and later dosing time points skip the infusion (twice weekly dosing schedule only) and resume SoA for the next scheduled infusion. • Hospitalization: at least 48 hours (see also Monitoring^d in the Specific Management section) • Dose modification: 
 – After elV infusion interruption > 24 hours restart at same or at lower dose after discussion with Amgen Medical Monitor. Refer to Section 6.2.2.3. – After IV interruption reduce to next lower dose level in Table 6-2 or discuss with Amgen Medical Monitor. For cohort 1, follow instructions of Section 6.2.2.3.5. • Additional measures: additional assessments as indicated in Section 6.2.2.3.4 	
If there is no improvement to CRS ≤ grade 1 within 7 days.
 
OR
 
Occurrence of grade ≥ 3 CRS with any subsequent dose

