
Grade	Description of Severity ^a	Interruption/ Delay	Specific Management	Restart Guidance	Permanent Discontinuation
Cytokine Release Syndrome continued (see Section 11.13 for additional guidance and grading scale details) (Short-term IV only)					
3	
Symptoms require and respond to aggressive intervention
 
 Oxygen requirement $\geq 40\%$, OR Hypotension requiring high dose^b or multiple vasopressors, OR Grade 3 organ toxicity or grade 4 transaminitis per CTCAE criteria 	Immediately interrupt / delay AMG 910 until event improves to CRS grade ≤ 1 .	
Admit to intensive care unit for close clinical and vital sign monitoring per institutional guidelines. Administer dexamethasone (or equivalent) IV at a dose maximum of 3 doses of 8 mg (24 mg/day). The dose should then be reduced step-wise. Additionally, tocilizumab^c should be administered at a dose of 8 mg/kg as a single dose and may be repeated once within 24 to 48 hours based on clinical assessment.
 
Monitoring^d following an event of CRS:
 
 the subject must be monitored for all subsequent dose administrations for a duration of time that is at least as long as the time it took for the onset of the last CRS plus 4 hours or per the protocol monitoring instructions, whichever is longer. also, considering the 2-week treatment free period after cycles 2 and 4, the subject must be monitored for dose 1 cycle 3 and dose 1 cycle 5 for a duration of time that is at least as long as the time it took for the onset of the last CRS plus 4 hours or per the protocol monitoring instructions, whichever is longer independent of non-occurrence of events in the prior treatment 
This monitoring requirement should be followed until there is no reoccurrence of CRS, at which time monitoring for subsequent doses should follow per protocol post-infusion monitoring. If a CRS occurs, then the event should be managed and monitored as per protocol, i.e., until it resolves to grade ≤ 1.
	
 Re-start possible if successfully managed and improved to \leq grade 1 within 7 days. Consult with Amgen Medical Monitor first. In case of infusion interruption, continue treatment with next planned dose, do not resume prior infusion or administer delayed infusion. For eIV infusion administration: Treatment initiation with eIV infusion should be restarted following the dosing schedule and SoA for cycle 1 day 1. This should be done at the earliest after 48 hours and under the supervision of the investigator or designee and premedication as described in Section 6.1.4 should be administered. Refer to Section 6.2.2.3. Delay of next infusion: 
 \leq 72 hours: follow the SoA for the cycle day on which the infusion was originally planned. The next infusions should then be administered in line with the planned dosing schedule. $>$ 72 hours: Starting with the cycle 1 day 8 infusion and later dosing time points skip the infusion (twice weekly dosing schedule only) and resume SoA for the next scheduled infusion. Hospitalization: at least 48 hours after resolution to \leq grade 2 (see also Monitoring^d in the Specific Management section) Dose modification: reduce to next lower dose level in Table 6-2 Additional measures: additional assessments as indicated in Section 6.2.2.3.4 	
If there is no improvement to CRS \leq grade 2 within 5 days and CRS \leq grade 1 within 7 days.
 
OR
 
If subject is still febrile or still on vasopressors within 8 hours after initiation of corticosteroid and tocilizumab
 
OR
 
In case of 2 separate grade 3 CRS events.

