2	Therapy or infusion interruption indicated but responds promptly to symptomatic treatment (eg, antihistamines, NSAIDS, narcotics, IV fluids); prophylactic medications indicated for ≤ 24 hours	Immediate interruption/delay until event has improved to grade ≤ 1	
Increase monitoring of vital signs as medically indicated until the subject is deemed medically stable
 
Monitoring^d following a grade 2 event of IRR:
 
 the subject must be monitored for all subsequent dose administrations (re-start and dosing thereafter) for a duration of time that is at least as long as the time it took for the onset of the last IRR plus 4 hours or per the protocol monitoring instructions, whichever is longer. also, considering initiation after the 2-week treatment free period after cycles 2 and 4, the subject must be monitored for a duration of time that is at least as long as the time it took for the onset of the last IRR plus 4 hours or per the protocol monitoring instructions, whichever is longer independent of non-occurrence of events in the prior treatment 
This monitoring requirement should be followed until there is no reoccurrence of IRR, at which time monitoring for subsequent doses should follow per protocol post-infusion monitoring.
 
If a subsequent IRR occurs, then the event should be managed and monitored as per protocol, i.e., until it resolves to grade ≤1.
	
 Re-start possible, if successfully managed and improvement to ≤ grade 1 in ≤ 14 days. Delay of re-start: 
 Re-start 7 days from cycle 1 day 1 at earliest Follow the SoA from cycle 1 day 1 onwards Hospitalization: at least 48 hours (see also Monitoring in the Specific Management section) Dose modification: resume at the same dose For next short-term infusion after the elV part consider slowing infusion rate to deliver the dose over 90 minutes Additional measures: additional assessments as indicated in Section 6.2.2.3.4 	
If not improved to ≤ grade 1 in ≤ 14 days
 
If event re-occurs at higher grade

Page 1 of 5

Abbreviations and footnotes defined on last page of table

Grade	Description of Severity	Interruption/ Delay	Specific Management	Re-start guidance	Permanent Discontinuation
Infusion-related Reaction (elV; continued)					

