2	
Symptoms require and respond to moderate intervention
 
 Oxygen requirement < 40%, OR Hypotension responsive to fluids or low dose of 1 vasopressor, OR Grade 2 organ toxicity or grade 3 transaminitis per CTCAE criteria 	
Immediately interrupt/delay AMG 910 until event improves to CRS grade ≤ 1.
 
eIV infusion: Avoid treatment interruption
	
Administer:
 
 Symptomatic treatment (eg, paracetamol/ acetaminophen for fever) Supplemental oxygen when oxygen saturation is < 90% on room air Intravenous fluids or low dose vasopressor for hypotension when systolic blood pressure is < 85 mmHg. Persistent tachycardia (eg, > 120 bpm) may also indicate the need for intervention for hypotension. If hypoxia or hypotension lasts > 24 hours manage as grade 3 CRS 
Monitor for CRS symptoms including vital signs and pulse oximetry at least Q2 hours for 12 hours and until resolution to CRS grade ≤ 1.
 
Investigators should consider use of tocilizumab^c as an additional therapy in this setting at a dose of 8 mg/kg as a single dose.
 
For subjects with extensive co-morbidities or poor performance status, manage per grade 3 CRS guidance below.
 
Monitoring^d following an event of CRS:
 
 the subject must be monitored for all subsequent dose administrations for a duration of time that is at least as long as the time it took for the onset of the last CRS plus 4 hours or per the protocol monitoring instructions, whichever is longer. 
This monitoring requirement should be followed until there is no reoccurrence of CRS, at which time monitoring for subsequent doses should follow per protocol post-infusion monitoring.
 
If a CRS occurs, then the event should be managed and monitored as per protocol, ie, until it resolves to grade ≤ 1.
	
 Re-start possible if successfully managed and improved to ≤ grade 1 within 7 days. Consult with Amgen Medical Monitor first. In case of infusion interruption, continue treatment with next planned dose, do not resume prior infusion or administer delayed infusion. For eIV infusion administration: In case the interruption does not exceed 24 hours, the infusion can be restarted at the same dose without additional measures. If the interruption exceeds 24 hours, the restart of the infusion should be performed under the supervision of the investigator or designee and premedication as described in Section 6.1.4 should be administered if implemented for start of eIV infusion. Delay of next infusion: 
 ≤ 72 hours: follow the SoA for the cycle day on which the infusion was originally planned. The next infusions should then be administered in line with the planned dosing schedule. > 72 hours: For the cycle 1 day 8 infusion and later dosing time points skip the infusion (twice weekly dosing schedule only) and resume SoA for the next scheduled infusion. Hospitalization: at least 48 hours (see also Monitoring^d in the Specific Management section) Dose modification: 
 After eIV infusion interruption > 24 hours restart at same or at lower dose after discussion with Amgen Medical Monitor After IV interruption reduce to next lower dose level in Table 6-2 or discuss with Amgen Medical Monitor. For cohort 1, follow instructions of Section 6.2.2.3.5. Additional measures: additional assessments as indicated in Section 6.2.2.3.4 	
If there is no improvement to CRS ≤ grade 1 within 7 days.
 
OR
 
Occurrence of grade ≥ 3 CRS with any subsequent dose

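### Table 6-4 omits the post-break monitoring bullet for CRS during the extended infusion, so cycle 5 day 1 can revert to 4 hours of observation

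*Protocol*

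**What the plan says.** Table 6-3 covers short-term infusions and Table 6-4 covers the eIV of cycle 1 week 1. The CRS heading in Table 6-3 limits its rows to short-term dosing and sends CRS during the eIV to Table 6-4.

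All eight grade 2 and 3 rows for IRR and CRS share a general rule. At later doses the subject is watched for the onset time of the last event plus 4 hours, or for the standard period if that is longer. The rule ends when the event stops recurring. In the CRS rows the release reads: "This monitoring requirement should be followed until there is no reoccurrence of CRS, at which time monitoring for subsequent doses should follow per protocol".

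Six rows add a second bullet for the first doses after the treatment-free intervals:
- Table 6-3 IRR, grades 2 and 3, and Table 6-4 IRR (eIV), grade 3: "also, considering the 2-week treatment free period after cycles 2 and 4, the subject must be monitored for a duration of time".
- Table 6-3 CRS, grades 2 and 3: "the subject must be monitored for dose 1 cycle 3 and dose 1 cycle 5 for a duration of time".
- Table 6-4 IRR (eIV), grade 2: "also, considering initiation after the 2-week treatment free period after cycles 2 and 4, the subject must be monitored".

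In all six the bullet holds "independent of non-occurrence of events in the prior treatment", so event-free doses before the break do not switch it off.

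The standard periods come from Tables 1-1 and 6-1. For cycle 5 day 1 the schedule says "Until 4 hours after EOI on day 1", and Table 6-1 makes this a minimum: "subject should be monitored intensely in hospital or outpatient clinic for at least 4 hours after end of each infusion". Hospital admission is not routinely required in cycle 5. For cycle 3 day 1 the stay is "Until 24 hours after EOI on day 1".

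**The concern.** The two rows without the second bullet are the Table 6-4 rows for CRS during the eIV, grades 2 and 3. They go from the general rule straight to its release. The eIV was introduced because of CRS in cohort 1 (Section 4.1), and Appendix 13 places the increased CRS risk in the first days after the initial infusion. The bullet is therefore missing for the period in which CRS is most expected.

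Appendix 13 also warns that infusion reactions and CRS may look alike at the bedside. Yet an eIV event recorded as IRR brings longer observation after each break, while the same picture recorded as CRS does not. The documents give no reason for the difference. At stake is how long a subject with known CRS on first exposure is watched when dosing resumes after about three weeks without drug.

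**Working it through.** **Row count.** 2 tables × 2 events × 2 grades = 8 rows.

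| Row | Post-break bullet |
|---|---|
| Table 6-3 IRR, grade 2 | present |
| Table 6-3 IRR, grade 3 | present |
| Table 6-3 CRS, grade 2 | present, names cycles 3 and 5 |
| Table 6-3 CRS, grade 3 | present, names cycles 3 and 5 |
| Table 6-4 IRR (eIV), grade 2 | present |
| Table 6-4 IRR (eIV), grade 3 | present |
| Table 6-4 CRS (eIV), grade 2 | absent |
| Table 6-4 CRS (eIV), grade 3 | absent |

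Present in 6, absent in 2.

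**Who is affected.** A subject has CRS during the eIV and none afterwards. The release sentence names no grade, so the condition is no later CRS of any grade. The general rule lapses and the standard schedule applies. If grade 2 or 3 CRS occurs at a short-term infusion, Table 6-3 takes over and its bullet covers the remaining breaks.

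**Hours.** The documents give no onset times, so these figures are illustrative. Let t be the onset in hours from the start of the eIV, and count monitoring from the end of the short-term infusion. The rule in the other six rows is max(standard, t + 4).

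- Cycle 5 day 1, standard 4 h: shortfall = (t + 4) − 4 = t.
- Cycle 3 day 1, standard 24 h: shortfall = max(0, t + 4 − 24) = max(0, t − 20).

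| Assumed t | Cycle 5 day 1: rule against text | Shortfall | Cycle 3 day 1: rule against text | Shortfall |
|---|---|---|---|---|
| 6 h | 10 h against 4 h | 6 h | 24 h against 24 h | 0 h |
| 20 h | 24 h against 4 h | 20 h | 24 h against 24 h | 0 h |
| 24 h | 28 h against 4 h | 24 h | 28 h against 24 h | 4 h |

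If t + 4 is instead counted from the start of the roughly 60-minute infusion, each non-zero shortfall is about 1 hour smaller. The tables do not say which clock is meant.

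**Drug-free gaps, with 2-week breaks.**
- Cycle 2 day 22 to cycle 3 day 1, weekly dosing: (29 − 22) + 14 = 21 days.
- Cycle 2 day 24 to cycle 3 day 1, twice-weekly dosing: (29 − 24) + 14 = 19 days.
- Cycle 4 day 22 to cycle 5 day 1, both schedules: (29 − 22) + 14 = 21 days.

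**Short-term infusions before cycle 5 day 1, if none is missed.**
- Weekly: 3 + 4 + 4 + 4 = 15.
- Twice-weekly: 6 + 8 + 4 + 4 = 22.

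**The case against.** **Grade 3 is nearly empty.** Related grade 3 CRS normally meets the dose-limiting toxicity definition (Section 6.2.1.3). Section 7.1 then requires discontinuation unless several conditions hold, clinical benefit among them. Benefit is hard to show in week 1, before the first scan at 6 weeks. Section 7.1 also allows restart under Table 6-3 criteria, but a subject restarting under Table 6-4 repeats the eIV one dose level lower and leaves after a second grade 3 CRS. This stands: the gap concerns grade 2 almost entirely.

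**The risk left is small.** A subject who reaches cycle 5 day 1 this way has had up to 15 or 22 short-term infusions without CRS. One of them was cycle 3 day 1, after an equal or nearly equal break and with a 24-hour stay. Section 6.1.4 may bring dexamethasone after a break, although it leaves later cycles to the investigator. A break extended to 3 weeks arguably triggers the 48-hour stay of Section 6.2.2.3.4. Four hours is a minimum. All of this stands, but the other six rows expressly decline to rely on event-free doses.

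**Intent is unclear.** The Table 6-3 CRS rows still contain eIV restart text, and a site might apply their bullet to any short-term dose after CRS. The pages between Section 6.2.2.3.4 and the grade 2 IRR row of Table 6-3 were not available, so a general rule there cannot be excluded. This stands as a limit. Against it, the Table 6-3 heading routes eIV events elsewhere.

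**The omission may be deliberate.** The reasons that suggest themselves do not fit. That the eIV is given only in week 1 does not explain why both IRR (eIV) rows keep the bullet. That eIV onset times do not carry over to short infusions does not explain why the CRS (eIV) rows already apply them to later doses. Table 6-4 also cites a footnote d that it does not define, which suggests incomplete copying. That is inference, not proof.

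**Practical reach.** SAP Section 7.1 records a decision to terminate the study early. This limits what an amendment could change here, not whether the tables agree.

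**Conclusion.** The inconsistency is real and can be checked on the page: 6 of 8 rows carry the bullet, and the two CRS (eIV) rows do not. As written, a subject with CRS during the eIV, almost always grade 2, and no later CRS returns to 4 hours on cycle 5 day 1. The shortfall against the other rows equals the onset time, so 6 to 24 hours for assumed onsets of 6 to 24 hours. Cycle 3 day 1 is short only if onset was later than 20 hours.

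A reader might infer more: that grade 3 subjects are exposed to the same extent, that both post-break doses are left at 4 hours, that the shortfall could run to the full length of the eIV, or that the sponsor chose weaker monitoring for CRS. The documents do not support these. Grade 3 is normally dose-limiting, and cycle 3 day 1 has a 24-hour stay. An onset late in a slow infusion does not translate into a realistic observation time after a 60-minute one. Nothing states an intent.

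The residual risk is modest, and the affected group is small and of unstated size. The row count is certain; the consequence rests on the Table 6-3 heading governing and on no contrary rule in the unavailable pages. The point is worth correcting but is not critical.

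**What to change.** In Table 6-4, add to the grade 2 and grade 3 CRS (eIV) rows the Table 6-3 bullet for dose 1 of cycles 3 and 5, including its clause that event-free doses do not cancel it. State that onset is timed from the start of the eIV and the monitoring period from the end of the short-term infusion. If the omission was intended, say so in the table. As an editorial matter, carry footnote d over to Table 6-4, which cites it.

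The drafting cost is one bullet in two rows and a sentence on timing. The operational cost is longer observation at up to two visits for a few subjects.
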